4. GENERAL ANALYSIS AND REPORTING CONVENTIONS

The following is a list of general analysis and reporting conventions to be applied to this study, unless otherwise specified. Departures from these general policies will be described, if applicable, in the appropriate sections of this SAP. When this situation occurs, the rules set forth in the specific section take precedence over the general policies.

All data displays (tables, listings, and figures) will have a header showing the sponsor company name, protocol number, page number, and display status (i.e. “DRAFT” or “FINAL”), as well as a footer indicating file name and run date/time. Summary tables and data listings will be summarized by active treatment versus placebo-treated patients (i.e., by treatment group) for efficacy and exposure, and by treatment group and overall otherwise. All data for analysis will be listed by-patient.

Categorical variables will be summarized using counts (n) and percentages (%) and will be presented in the form “n (xx.x).” If a count is 0, 0% will be shown for the percentage. If a percentage is 100%, 100.0% will be shown. To ensure completeness, summaries for categorical variables will include all categories, even if no patients had a response in a particular category. Unless otherwise specified, the denominator for each percentage will be based on the number of patients in the population being summarized (header n). Percentages will be rounded to one decimal place.

Continuous variables will be summarized using mean, standard deviation, minimum, maximum, median, and number of patients. The minimum and maximum will be the same precision as the original collected data. The mean and median will be reported to an additional level of precision than the original observations, and the standard deviation will be reported to two additional levels of precision than the original observations. The precision for some original collected data and derived variables are longer than required for clinical interpretation (eg, >15 decimals). In these situations, the number of decimal places will be determined by the table of precision included as an attachment.

Results of statistical models (ie, least-squares means, confidence intervals, risk differences) will be rounded to two decimal places. Standard error will be reported to an additional level of precision. Results which cannot be determined will be displayed as “NA”, “NE”, or similar.

For tests of hypothesis of treatment group differences, the associated p-value will be reported in rounded format. All p-values will be rounded to four decimal places after assignment of statistical significance; p-values that round to 0.0000 or are reported by SAS as zero will be presented as “≤0.0001”; p-values that round to 1 or are reported by SAS as 1 will be presented as “>0.9999”. P-values which are significant at a 0.05, 0.025, 0.01, 0.001, or 0.0001 level will be marked with asterisks. P-values which cannot be determined will be displayed as “NA”. P-values are descriptive for outcomes and analyses not included in the multiplicity algorithm.

Date of last dose is collected on the *Treatment Discontinuation/Completion* eCRF page. For patients with missing or partial date of last dose, the date of last dose (ie, treatment end date) will be imputed. Date of last dose will be imputed as follows:

Concert Pharmaceuticals, Inc.
Statistical Analysis Plan – CP543.3001

- Derive the number of tablets taken at the last visit as the dispensed amount minus the returned amount. For treatment compliance (Section 7.3) and exposure (Section 9.2), if the returned amount is missing, it will be assumed that zero tablets were taken. Otherwise, it will be assumed that 60 tablets were taken.
- An estimated date of possible last dose will be calculated by adding the number of tablets taken divided by 2 to the visit date associated with the last visit where drug accountability was collected.
- If there is a partial date of last dose, missing day will be imputed using the day from treatment start date, or the last day of the month if that month has fewer days than the treatment start month.
- Treatment end date will be the minimum of the partial date of last dose, calculated estimated date of possible last dose, and collected study discontinuation/completion date.

Summary tables and data listings:

- Unless otherwise specified, no preliminary rounding will be performed; rounding will only occur after analysis.
- Data from patients excluded from an analysis population will be presented in the data listings but will not be included in the calculation of summary statistics, where applicable.
- Data from each patient will be separated by a blank line. Within a data listing, if a descriptive item appears line after line (e.g., repetition of a patient number, date, visit, etc.), only the first occurrence will be displayed (e.g., in Listing of Vital Signs, patient number, date and visit will only be displayed on first row when presenting all parameters collected at same visit). Repetition of actual results or outcomes (e.g., adverse events, lab results, vital sign values, etc.) will not be collapsed.
- Data listings will be sorted by treatment, patient, and date and/or time of assessment, as applicable.
- When change from baseline or change to baseline is calculated, baseline is the last observation obtained prior to first dosing of the study drug.
- Unless otherwise noted, values reported as greater than or less than some quantifiable limit (e.g., “< 2.0”) will be summarized as using the numeric equivalent in summary tables and figures (e.g. “<2.0” will be analyzed as 2.0). The reported value will be used in listings.

Mock tables and data listings will be provided as attachments to this analysis plan. Minor changes to the mocks after formal SAP approval will not necessitate re-approval unless changes to the text of the SAP are required.

Concert Pharmaceuticals, Inc.
Statistical Analysis Plan – CP543.3001

All statistical deliverables will be produced, validated, and reviewed for accuracy/consistency in accordance with [REDACTED] standard operating procedures and the processes described in the statistical validation plan.

SAS® (SAS Institute, Cary, North Carolina) statistical software, version 9.4 or later, will be used for all analyses. Adverse Events and Medical History will be coded in Medical Dictionary for Regulatory Activities (MedDRA) Version 23.1. Concomitant medications will be coded in World Health Organization (WHO) Drug Version 2020-SEP and Anatomical-Therapeutic-Chemical (ATC) classification and preferred term.

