7.3. Measures of Treatment Compliance

Patients will strive for 100% compliance with the daily dosing schedule. Treatment compliance will be summarized as percent of planned dose received for each dosing regimen. Percent of planned dose received will be calculated for the entire treatment period as follows:

100*(Tablets Dispensed-Tablets Returned)/(Tablets Expected)

Tablets Expected is defined as the time on treatment multiplied by the expected number of pills taken daily (x2 for the 12 mg BID group; x2 for the 8 mg BID group; x2 for the placebo group), where time on treatment is defined as treatment end date – treatment start date + 1. Dose interruptions will be ignored in this calculation. Derived patient compliance, compliance per the

Concert Pharmaceuticals, Inc.
Statistical Analysis Plan – CP543.3001

eCRF (80% or higher versus less than 80%), and dosing exceptions will be listed in by-patient data listings.

For patients who roll over into one of the open label extension studies, it will be assumed that only 1 dose of study drug was administered for the last dose of study drug. For patients who do not roll over, it will be assumed that 2 doses of study drug were administered for the last dose of study drug.

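### For patients without a complete last-dose date, SAP Section 4 counts an unreturned bottle as 60 tablets in the end date but 0 in the dose, and can count a returned bottle's tablets twice

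*SAP*

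**What the plan says.** SAP Section 4 limits the rule to incomplete dates: "For patients with missing or partial date of last dose, the date of last dose (ie, treatment end date) will be imputed". It then works in steps.

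- Tablet count: "Derive the number of tablets taken at the last visit as the dispensed amount minus the returned amount".
- Missing return: "For treatment compliance (Section 7.3) and exposure (Section 9.2), if the returned amount is missing, it will be assumed that zero tablets were taken". The next sentence reads "Otherwise, it will be assumed that 60 tablets were taken".
- Estimated last dose: found by "adding the number of tablets taken divided by 2 to the visit date associated with the last visit where drug accountability was collected".
- Final step: "Treatment end date will be the minimum of the partial date of last dose, calculated estimated date of possible last dose", with the study discontinuation or completion date as the third candidate.

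The result feeds two later sections. In SAP Section 7.3, compliance is tablets dispensed minus returned, divided by tablets expected. Tablets expected is two per day over the time on treatment, and "time on treatment is defined as treatment end date" minus start date plus one. In SAP Section 9.2, days in study run to the same end date, while cumulative dose is tablets taken times tablet strength.

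The schedules in both documents mark drug accountability at Weeks 4 to 24 and not on Day 1. Protocol Section 9.3 describes it as a comparison of dispensed with returned tablets. Protocol Section 9.4.2 supplies one 60-count bottle at each four-week visit.

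**The concern.** The two defects concern different patients.

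The first is the bottle that never comes back. A known return is already handled by subtraction, so the 60-tablet sentence can only govern the end date. The same bottle then adds 30 days to the compliance denominator and to exposure, and nothing to the compliance numerator or the cumulative dose. Either count could be defended as a convention. Using both in one ratio cannot.

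The second is the bottle that does come back. The tablets missing from it were taken before the return visit. Adding them to that visit's date moves the last dose into a period when the patient had none of those tablets left.

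The end date drives days in study, dosed days and compliance. If the imputed date is used there, it also affects the time-to-treatment-termination curve (SAP Section 6.1), the choice of on-treatment laboratory values (Section 9.5) and the Week 12 to 24 adverse event denominator (Section 9.3).

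**Working it through.** The plan gives no figure of its own to reproduce, so I applied its rules to example patients.

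**Inputs.** Visits fall on the target days of SAP Table 2: Days 1, 29, 57, 85, 113, 141, 169 and 197. Dosing is two tablets a day, so a four-week interval uses 56 tablets and 60 tablets last 60/2 = 30 days. Compliance = 100 × tablets / (2 × days to the end date). I ignore the Section 7.3 convention of a single last-day dose for roll-over patients, which changes the expected count by one tablet.

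**1. Last bottle not returned.** Assume full adherence before that bottle, study end on Day 169, and that the last visit with accountability is the one at which the bottle was dispensed. The end date under the 60-tablet assumption is the dispensing day plus 30, capped at Day 169. Under a consistent zero it is the dispensing day itself.

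| Bottle dispensed | Tablets before it | End date (60) | 0 in numerator, 60 in end date | 60 in both | 0 in both |
|---|---|---|---|---|---|
| Week 4, Day 29 | 56 | Day 59 | 56/118 = 47.5% | 116/118 = 98.3% | 56/58 = 96.6% |
| Week 8, Day 57 | 112 | Day 87 | 112/174 = 64.4% | 172/174 = 98.9% | 112/114 = 98.2% |
| Week 12, Day 85 | 168 | Day 115 | 168/230 = 73.0% | 228/230 = 99.1% | 168/170 = 98.8% |
| Week 16, Day 113 | 224 | Day 143 | 224/286 = 78.3% | 284/286 = 99.3% | 224/226 = 99.1% |
| Week 20, Day 141 | 280 | Day 169 (171 capped) | 280/338 = 82.8% | 340/338 = 100.6% | 280/282 = 99.3% |

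Exposure and dose also disagree. In the Week 4 case the patient has 59 days of exposure but tablets for 28 days. On 12 mg the cumulative dose is 56 × 12 = 672 mg, against 116 × 12 = 1392 mg if the bottle was taken.

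**2. Last bottle returned, patient stays on study.** Last dose Day 70, bottle dispensed Day 57 and returned Day 85, follow-up to Day 169. Tablets from the last bottle: 28. Total tablets: 56 + 56 + 28 = 140.

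- Anchor at the return visit: 85 + 28/2 = Day 99, which is 29 days late. Compliance is 140/198 = 70.7%.
- Anchor at dispensing: 57 + 14 = Day 71. Compliance is 140/142 = 98.6%.
- True values: Day 70 and 140/140 = 100%.

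With Day 99 as end date, this patient would also count as dosed after Week 12 (Day 85), which did not happen.

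**3. What the existing minimum does.** Take a patient who completes Week 24, with 336 tablets taken in all and 56 from the last bottle. The return-visit estimate is 169 + 28 = Day 197.

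- Enters the extension, study completion Day 169: the minimum gives Day 169 and 336/338 = 99.4%. The error is gone.
- Exits at Week 28, study completion Day 197: the end date stays at Day 197 and compliance is 336/394 = 85.3%. The dispensing anchor gives 141 + 28 = Day 169 and 99.4%.

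**The case against.** The strongest defence of the tablet rule is that both sentences sit inside the date imputation. They might mean zero tablets when the date serves compliance and exposure, and 60 when it serves anything else. Numerator and denominator would then agree, and the Week 4 case would be 96.6%. But Section 4 defines one treatment end date, and Sections 7.3 and 9.2 refer to one. Nothing in the text sets up two end dates per patient.

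The defence of the anchor is stronger. Section 4 never says return visit, and Weeks 4 to 20 are also dispensing visits. If accountability records are keyed to the visit that dispensed the bottle, adding half the tablets is correct. For a bottle never returned, the last accountability visit normally is the dispensing visit, so the anchor is sensible there. The second defect therefore rests on the literal text read with the schedule, and only for a returned bottle.

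The minimum is a real safeguard. It removes the second error for patients who leave or roll over at that visit, and a partial date may limit either error. It does not help patients who stop drug but stay on study, as Protocol Section 8.3 intends, or completers who exit at Week 28.

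Two stronger readings are tempting and not supported:

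- A reader might infer that the rule makes patients fail an 80% compliance cut. In SAP Section 7.3 that split is an eCRF field listed beside derived compliance, and in Protocol Section 9.3 it is a retraining trigger. No planned analysis divides derived compliance at 80%.
- A reader might infer 0% compliance when the first bottle is never returned. No accountability visit precedes Week 4, so the rule has no date to add to. The result is undefined, not zero.

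**Conclusion.** Both defects stand, for patients with a missing or partial last-dose date only. The documents do not say how many there will be.

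The tablet conflict is the firmer of the two, because it follows from the natural reading of Section 4 with Sections 7.3 and 9.2. It lowers derived compliance to between 47.5% and 82.8%, where either consistent assumption gives about 97% to 101%. That range assumes full earlier adherence, visits on target days and study end on Day 169.

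The anchor error depends on reading the accountability visit as the return visit. In the examples it moves the end date about four weeks late and takes compliance from 98.6% to 70.7%, or from 99.4% to 85.3%.

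A reader might conclude that exposure and compliance are wrong for the trial as a whole, or that efficacy is affected. Neither follows. A collected, complete last-dose date bypasses the rule, and the primary efficacy analysis does not use the treatment end date. This is a minor point that is worth correcting because the correction is easy.

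**What to change.** Amend SAP Section 4 as follows.

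- Anchor the estimate to the date the last bottle was dispensed. If that bottle was returned, cap the estimate at the return visit as well. Keep the existing minimum with the partial date and the study discontinuation or completion date. This also supplies a date when a first bottle is never returned.
- Choose one tablet count for an unreturned bottle and use it in the end date, the compliance numerator and the cumulative dose. The other count can be shown as a sensitivity summary.

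The cost is two sentences and one derivation. Protocol Section 9.4.5 already requires the date and amount of each dispensing to be recorded.

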Patients will take the first dose of study drug in the clinic on Day 1 and will be instructed to take study drug daily approximately every 12 hours for the duration of the Treatment Period. Patients should dose study drug in the clinic on all Study Visit Days after clinical laboratory blood draws are completed. Other baseline assessments will include patient and clinician global impression of disease severity (PGI-S and CGI-S), Patient Reported Outcome for Satisfaction (SPRO) and Hair Quality (QPRO), the Hospital Anxiety and Depression Scale (HADS), and assessments for eyelash and eyebrow involvement. The schedule of assessments can be found in Appendix [15.2](#).

The double-blind, placebo-controlled Treatment Period will last 24 weeks. Assessment of treatment response using SALT for efficacy will occur at 4, 8, 12, 16, 20 and 24 weeks.

Patient safety will be monitored throughout the trial by the Investigator and supported by regular review by the Medical Monitor and DMC. Chemistry and hematology laboratory values will be assessed under fasted conditions bi-weekly for the first month of the treatment period, followed by every 4 weeks through the remainder of the study. Lipid levels will be assessed every 4 weeks throughout the Treatment Period. In light of the COVID-19 pandemic, challenges in the

Concert Pharmaceuticals, Inc.
Statistical Analysis Plan – CP543.3001

conduct of study visits may arise from quarantines, site closures, and/or travel limitations. To ensure the safety of trial participants and to minimize risk to trial integrity, alternative methods for drug dispensation and assessments, including telemedicine visits and clinical laboratory blood draws at a local laboratory or via a Home Health Care agency, may be offered for those trial participants who may no longer have access to the investigational site. Significant cytopenias or other hematologic abnormalities will be managed by severity through dose interruption or discontinuation, and signs and symptoms of infection will be closely monitored and treated promptly. Patients who experience intolerable symptoms during treatment may discontinue treatment at the judgement of the Investigator, but will be followed for safety and efficacy assessments until Week 24, unless they withdraw consent. Patients may withdraw consent at any time.

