9.5. Clinical Laboratory Evaluation

Clinical laboratory samples should be collected at the beginning of each clinic visit and just prior to a dose on all Study Visit Days and will be processed by a central laboratory. In the event a patient is unable to attend an in-clinic visit due to COVID-19, clinical laboratory blood draws may be performed by a Home Health Care agency or a local laboratory.

Clinical laboratory variables will be presented in 3 ways. First, change from baseline to the minimum post-baseline value, maximum post-baseline value, and final on-treatment value will be summarized. Baseline will be defined as the laboratory value obtained before the first dose of study drug on Day 1; if Day 1 values are unavailable, then values obtained at the Screening Visit will be used. Only post-baseline values on treatment will be eligible. The Follow-up Visit will be excluded from possible minimum, maximum, or final post-baseline values.

This analysis will be repeated with outlying values removed from eligibility for minimum and maximum values. An outlier is defined using the interquartile range (IQR). The IQR is equal to the third quartile minus the first quartile and will be calculated by visit and treatment group for each numeric parameter. The IQR will be multiplied by a constant of 1.5. Any value which is above 1.5 times IQR plus the third quartile or below 1.5 times IQR minus the first quartile will be considered an outlier and will be removed from eligibility for minimum, maximum, or final post-baseline values.

Second, shift tables will summarize the number and percentage of patients with categorical changes from baseline defined by the laboratory normal reference range for each laboratory parameter (Below reference range, Within reference range, and Above reference range). The baseline category will be cross-tabulated with post-baseline category (3×3 table). The post baseline category will be assigned and summarized in 2 ways for each laboratory parameter: minimum post-baseline value and maximum post-baseline value. Only post-baseline values on treatment will be eligible. Patients will only be reported in the shift tables if they have both a baseline and post-baseline value.

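### For a last-dose date with the day missing, the SAP's minimum rule has no lower bound, so the imputed treatment end date can be too early and distort exposure and compliance (minor)

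*SAP*

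**What the plan says.** SAP section 4 limits the rule to incomplete dates: "For patients with missing or partial date of last dose, the date of last dose (ie, treatment end date) will be imputed". For a partial date, "missing day will be imputed using the day from treatment start date"; a month too short to contain that day gets its final day instead. The three candidate dates are then combined: "Treatment end date will be the minimum of the partial date of last dose, calculated estimated date of possible last dose", with the date of study discontinuation or completion as the third. The tablet-based candidate is the date of the last visit with drug accountability plus tablets taken divided by 2, so it cannot precede that visit. Section 4 sets no lower bound from the last visit, the last documented dose or the tablet count.

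The result is used directly in two places. In SAP 7.3, "time on treatment is defined as treatment end date" minus start date plus 1, and Tablets Expected is that number times 2. In SAP 9.2, days in the study is end minus start plus 1, and days dosed is the same quantity less dosing exceptions. Neither section corrects an end date that is too early. SAP section 3 adds that "Patients should dose study drug in the clinic on all Study Visit Days", so the visit schedule points to days on which a patient still on drug would have taken a dose.

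**The concern.** A minimum of three dates is a sensible guard against an end date that is too late. It gives no protection against one that is too early, and the start-day fill can be too early by up to 30 days. When that happens, the later evidence (the tablet count and the study discontinuation date) cannot pull the date forward, because the minimum discards it.

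The error has a direction. It shortens exposure and raises compliance above 100%, and it does so whenever the fill-in date precedes the true last dose. It does not depend on the clause for short months, and it remains if the tablet arithmetic is tidied up.

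**Working it through.** The documents state no figure for this rule, so there is none to reproduce. The check applies the rule to calendar dates.

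**Inputs.**
- Imputation rule: SAP section 4.
- Visit targets at Days 1, 15, 29, 57, 85, 113, 141 and 169: SAP 8.1.2, Table 2.
- Two tablets per day: SAP 7.3.
- Assumed: the other two candidate dates fall no earlier than the true last dose.

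**Notation.** S is the first-dose date. P is the day of the month of S placed in the recorded month of last dose. End date = min(P, tablet-based date, study discontinuation date). Time on treatment = end − S + 1. Compliance = 100 × tablets used / (2 × time on treatment).

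**Case 1: last dose in the start month.** P equals S. The other candidates cannot precede S, so the end date equals S and time on treatment is 1, whatever the tablet count shows.
- Example: first dose 3 March, last dose recorded as March, 40 tablets used.
- Tablets Expected = 2 × 1 = 2. Compliance = 100 × 40/2 = 2000%.
- Forty tablets at two per day from 3 March run to 22 March, which is 20 days.
- Days in the study is 1. Days dosed is 1 less any dosing exceptions, so it can fall below 1 or become negative.

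**Case 2: last dose in a later month.** First dose 3 March 2021, Week 12 dose on 26 May (Day 85), true last dose 28 May (Day 87), recorded as May 2021.
- P = 3 May 2021 = Day 62, which is 23 days before the Week 12 dose.
- Tablets used = 87 × 2 = 174. Tablets Expected = 62 × 2 = 124. Compliance = 100 × 174/124 = 140%.
- March and May both have 31 days, so the short-month clause plays no part.

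**How often, among partial dates.** Grid of 365 start dates (1 October 2020 to 30 September 2021) by every last-dose day from 1 to 169, which is 61,685 combinations, with visits on target.
- Same-month: 5,738 (9.3%). All give 1 day; in 5,373 the true duration was longer. Leaving out a Day 1 stop gives 5,373/61,320 = 8.8%.
- End date before the last scheduled clinic dosing visit: 4,015 (6.5%), mean gap 17.6 days, maximum 28.
- Overlap: 1,720 of those 4,015 (43%) are same-month cases. The later-month cases are 4,015 − 1,720 = 2,295, which is 3.7% of all combinations.
- End date before first dose: 0. The missing bound is at the last known dose, not at the start.

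**The case against.** The strongest reply is that this is an edge case in descriptive tables. Complete dates are untouched, the documents give no count of partial ones, and the grid percentages rest on assumed uniform timing, on-target visits and a dose at every visit. That stands, and it limits the priority.

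Several stronger readings are tempting and the documents do not support them.
- A reader might infer that anyone who stops in the month of starting gets one day of exposure. This holds only when the day of last dose is missing.
- A reader might infer that laboratory values drawn on drug are reclassified as off treatment. SAP 9.5 says "Only post-baseline values on treatment will be eligible" for the change summaries and shift tables, but it does not define on treatment by the imputed end date, and the only visit it names for exclusion is the Follow-up Visit. Its definition of treatment-emergent Grade 3 or 4 values does not repeat the restriction.
- A reader might infer that the Kaplan-Meier curve of early treatment termination is distorted. SAP 6.1 uses the date of last treatment to censor completers and does not say that early terminators are timed by the imputed date.
- A reader might add 9% and 6.5%. They overlap; same-month plus later-month is about 9.3% + 3.7% = 13.0% of partial dates.

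It is also fair to object that a floor at the last clinic visit would be unsafe. The schedule lists dispensing and accountability but no record of the clinic dose. Protocol 8.3 keeps patients who have stopped drug on the visit schedule, and visits may be remote. Attendance is therefore not proof of dosing, and the floor has to rest on something recorded.

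None of this rescues the rule as written: a same-month partial date still gives a one-day treatment period in the face of a tablet count that shows otherwise.

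**Conclusion.** The rule is wrong as written for last-dose dates with month and year known and day missing. In the start month the error is certain whenever true treatment lasted more than a day: time on treatment and days in the study equal 1. In later months the end date can fall before a day on which the patient was still on drug, by up to 28 days in the grid.

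The certain effect is on compliance (SAP 7.3) and exposure (SAP 9.2). An effect on the Kaplan-Meier curve or on the on-treatment laboratory change and shift tables follows only if those are programmed from the imputed end date, which the SAP does not say. The primary efficacy analysis does not use this date. The grid shares describe how the rule behaves among partial dates; they do not predict how many patients are affected, which is probably few. Priority: minor.

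**What to change.** In SAP section 4, make two additions.

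1. Floor the imputed end date at the last date with recorded evidence of dosing, such as drug accountability or dosing-exception records, and not at visit attendance alone. Cap the result at the end of the recorded month and at the study discontinuation date.
2. When the recorded last-dose month is the start month, do not use the start day. Use a tablet-based date counted from the dispensing date of the last bottle, limited to the recorded month. In Case 1 this gives 22 March. Counting from the return visit would not work: with accountability at Week 4 (31 March), adding 40/2 = 20 days gives 20 April, which the month limit cuts to 31 March, 9 days late.

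The cost is a short SAP text change and a small edit to the exposure program. The team should first confirm which records carry dated evidence of dosing. The floor alone improves average accuracy only modestly: in a simulation with start dates uniform over 9 months and last dose uniform over Days 2 to 169, mean absolute error fell from 10.1 to 9.0 days. Its purpose is to remove impossible dates.
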